Study Objectives	To determine the efficacy and safety of ascending oral albendazole dosages in children and adults infected with T. trichiura and in children and adults infected with hookworm. In preschool-aged children: (i) 200 mg, (ii) 400 mg and (iii) 600 mg; and in schoolchildren and adults: (i) 200 mg (only for hookworm infections), (ii) 400 mg, (iii) 600 mg and (iv) 800 mg will be compared against both parasites (T. trichiura and hookworm). Additionally, albendazole disposition will be measured in children and adults using a microsampling device.			
	Our primary objective is to determine the dose-response base on cure rates of albendazole in (i) preschool-aged children (2-years), (ii) school-aged children (6-12 years) and (iii) adults (≥ 2 years) infected with T. trichiura and in (i) preschool-aged children (2-5 years), (ii) school-aged children (6-12 years) and (iii) adult (≥ 21 years) infected with hookworm.			
	The secondary objectives of the trial are:			
	a) To determine the efficacy based on egg reduction			
L	Page 8 of 36			

	rates of albendazole in preschool-aged children, school-aged children and adults; b) To determine an exposure (including Cmax, AUC and tmax)-response correlation of albendazole in preschoolaged (2-5 years), school-aged children (6-12 years), and adults (≥ 21 years); c) To evaluate the safety and tolerability of albendazole in preschool-aged children, school-aged children and adults; and d) To determine the efficacy against concomitant soil-transmitted helminthiasis (Ascaris lumbricoides) e) To assess genetic heterogeneity in hookworm and T. trichiura populations with regard to the efficacy of different doses of albendazole.		
Study design	Single blind, randomized controlled trial (participants and lab technicians are blinded)		
Study product / intervention	Administration of a single oral dose of albendazole		
Comparator(s)	Matching placebo (purchased from Fagron)		
Key inclusion / Exclusion criteria	Inclusion: preschool-aged children (2-5 years), school-aged children (6-12 years) and adults (≥21 years) infected with T. trichiura or hookworm, absence of major systemic illnesses, written informed consent signed by parents and/or caregivers for minors; and oral assent by school-aged children. Exclusion: Any abnormal medical conditions or chronic disease, negative diagnostic result for T. trichiura and hookworm, pregnancy, no written informed consent.		

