standardized questionnaire (for preschool-aged children this will be administered to the caregiver of the child). In addition a clinical examination will be performed by the study physician and venipuncture to examine biochemical parameters in the blood will be carried out by study nurses before treatment. Adults, children and caregivers of preschool-aged children will also be interviewed before treatment, 3 and 24 hours after treatment, and at follow-up (2-3 weeks after treatment) about the occurrence of adverse events. The efficacy of the treatment will be determined 14-21 days post-treatment by collecting another two stool samples. All stool samples will be examined with duplicate Kato-Katz thick smears. A subsample of children and adults will be sampled using finger pricking for micro-blood sampling at 0, 1, 2, 3, 4, 6, 8, 24 hours post-dosing to evaluate pharmacokinetic parameters. **Statistical Analyses** An available case analysis (full analysis set according to the intention to treat principle) will be performed, including all subjects with primary endpoint data. Supplementary, a per-protocol analysis will be conducted. CRs will be calculated as the percentage of egg-positive subjects at baseline who become eggnegative after treatment. Geometric mean egg counts will be calculated for the different treatment arms before and after treatment to assess the corresponding ERRs Bootstrap resampling method with 5,000 replicates will be used to calculate 95% confidence intervals (CIs) for ERRs. E_{max} models using the DoseFinding package of the statistical software environment R will be implemented to predict the dose-response curves in terms of CRs and ERRs. Noncompartmental and nonlinear mixed-effects (NLME) modeling will be used to determine PK parameters. **GCP** statement This study will be conducted in compliance with the protocol, the current version of the Declaration of Helsinki, ICH-GCP E6 (R2) guidelines as well as all national legal and regulatory requirements. **Key explanation for the** This study will be carried out in children, since an infection with T. inclusion of children trichiura and hookworm occurs most often in children and they are the main targets of preventive chemotherapy programs. Moreover, the exact dosage of albendazole in preschool and school-aged children has not yet been determined. Recruitment procedure Participants will be recruited from rural communities situated in Côte d'Ivoire and identified to have at least a moderate infection risk (prevalence: 10-49%) of *T. trichiura* or hookworm.

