4.4. Measure to minimize bias

Study participants eligible for treatment will be randomly assigned to one of the treatment arms using a computer-generated, stratified block randomization code. The random allocation sequence with varying random blocks of 4 and 8 (or 5 and 10, respectively) stratified by 2 levels of baseline infection intensity (light and moderate *T. trichiura* and hookworm infections) will be provided by a statistician. Study-site investigators will be aware

of the study group assignment, whereas participants and laboratory technicians will be blinded.

Placebo controlled trials reduce the risk of potential bias that can also interfere with the observed outcomes. In previous studies (e.g. Coulibaly et al. 2017 Lancet Global Health), we have observed moderate cure and egg reduction rates in placebo treated children likely due to the low sensitivity of anthelminthic diagnostics. Children treated with placebo will be treated at follow up (3-weeks post treatment) with 400 mg albendazole. This treatment delay does not cause any harm.

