7.2. Justification of number of trial subject

Since the existence of a drug effect is well known, the main aim of the study is the elucidation of the nature of the dose–response relationship. A series of simulations was carried out to determine the required sample size. We assumed a true cure rate against hookworm of 5%, 30%, 50%, 70% and 80% (for 0, 200, 400, 600 and 800 mg) and of 5%, 10%, 20%, 30% and 40% against *T. trichiura* and loss to follow up of 5%. We estimated that enrolling 40 participants per arm will be sufficient to predict the dose response curve with a precision (defined as median distance between prediction and confidence band) of about 10 percentage points. The suggested sample size is also in line with the recommendations from Klingenberg et al. 2009 [11]. This sample size is sufficiently high to determine the key PK parameters as well as PK/PD relationships.

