7.3. Description of statistical methods

The primary analysis will use the full analysis set (available case population) according to the intention to treat principle defined as all randomized subjects which provide any follow-up data. Only subjects which were negative at baseline and erroneously randomized will be excluded from the analysis. In addition, a per-protocol analysis will be conducted. CRs will be calculated as the percentage of egg-positive participants at baseline who become egg-negative after treatment. EPG will be assessed by adding up the egg counts from the quadruplicate Kato-Katz thick smears and multiplying this number by a factor of six. The ERR will be calculated (ERR = (1-(mean at follow-up/mean at baseline))*100).

Geometric mean egg counts will be calculated for the different treatment arms before and after treatment to assess the corresponding ERRs. Bootstrap resampling method with 5,000 replicates will be used to calculate 95% confidence intervals (CIs) for ERRs point estimates. E_{max} models using the DoseFinding package of the statistical software environment R will be implemented to predict the dose-response curves in terms of CRs and ERRs.

On the basis of the LC-MS/MS measurements, the following PK parameters for plasma will be calculated:

C_{max} maximal plasma concentration

t_{max} time to reach C_{max}

AUC area under the curve, from 0 to 24h and 0 to inf

T_{1/2} elimination half-life

 C_{max} and T_{max} will be observed values derived from the plasma concentration time profile. AUC and $T_{1/2}$ will calculated with the software WinNonlin (Version 5.2, Pharsight Corporation, USA) using noncompartmental analysis. The elimination half-life will be estimated by the equation: $T_{1/2} = ln2/\lambda$, where λ will be determined by performing a regression of the natural logarithm of the concentration values during the elimination period.

Further PK analysis will be undertaken fitting a structural compartmental PK model with the software NONMEM 7 via nonlinear mixed effects modeling (allowing for both between patient variation and random effects). This model will describe the blood drug levels in time, allowing one to investigate variation between patients in drug levels. In addition, pharmacometric-pharmacodynamic (PKPD) analysis will be undertaken via NONMEM to investigate the drivers of cure and/or burden reduction and potentially any covariates with drug levels.

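### Does leaving the Emax scale, form and ED50 limit open in section 7.3 put the dose-response result at risk?

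*Combined protocol and SAP*

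**What the plan says.** Section 7.3 and the Statistical Analyses entry of the Synopsis each give the dose-response model one sentence: Emax "models using the DoseFinding package of the statistical software environment R will be implemented to predict the dose-response curves", for cure rates and egg reduction rates. Neither place states a response scale, a 3-parameter or sigmoid form, limits on ED50, or least squares against likelihood. No curve of another shape is planned. The two added analyses, per-protocol and double infections, change the population and not the model. Section 7.3 also plans the observed cure rate, as a percentage of those egg-positive at baseline.

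Section 7.2 states that "the main aim of the study is the elucidation of the nature of the" dose-response relationship. Its simulations assume a "true cure rate against hookworm of 5%, 30%, 50%, 70% and 80" per cent at 0, 200, 400, 600 and 800 mg, and rates "of 5%, 10%, 20%, 30% and 40% against" *T. trichiura*. With 40 per arm and 5% loss to follow-up it expects a "precision (defined as median distance between prediction and confidence band) of about 10 percentage points". It does not say which model was fitted in those simulations.

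**The concern.** The curve is the main product of the trial, and section 2 calls the 400 mg dose empirical, so the rise above 400 mg is a result that readers will look for. A hyperbolic Emax curve on the cure-rate scale can only flatten with dose, while the *T. trichiura* planning rates steepen. On the logit scale the same form fits *T. trichiura* well but flattens hookworm too soon. Different analysts could therefore report different gains from the same data.

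Section 4.4 says that study-site investigators will be aware "of the study group assignment, whereas participants and laboratory technicians will be blinded", so the model could be chosen with results by arm in view. The 10-point precision criterion measures band width and would not reveal a bias from the choice of form.

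**Working it through.** **Inputs.** Planning rates, 40 per arm and 5% loss come from section 7.2: 40 × 0.95 = 38 evaluable. Arms come from section 3: *T. trichiura* school-age/adult 0, 400, 600, 800 mg; hookworm school-age/adult 0, 200, 400, 600, 800 mg; preschool, both parasites, 0, 200, 400, 600 mg. Assumed, because the documents give none: a wide ED50 limit of 20 times the top dose for 3-parameter fits; for sigmoid fits, Hill exponent 0.5 to 10 and ED50 up to 1.5 times the top dose.

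**The plan's own figures.** Hookworm has 4 + 5 + 5 = 14 arms and *T. trichiura* 4 + 4 + 4 = 12; 26 × 40 = 1040, as stated. Simulated median half-widths of the curve, with ED50 limited to 1.5 times the top dose, are 7.6–8.8 points (hookworm school-age/adult) and 8.4–10.2 (*T. trichiura* school-age/adult) for the 3-parameter form. For the sigmoid form they are 9.8–11.7 and 11.4–11.8. Preschool cohorts give 6.6–13.5. The stated precision of about 10 points reproduces overall.

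**Why one fit is biased.** *T. trichiura* school-age/adult rises (20 − 5)/400 = 0.0375 points per mg up to 400 mg, then (40 − 20)/400 = 0.05. A hyperbolic Emax on the cure-rate scale cannot steepen; its limit is a straight line. The least-squares line through (0, 5), (400, 20), (600, 30), (800, 40) has slope 152.5/35 = 4.36 points per 100 mg, a gain of 4 × 4.36 = 17.4 against a true 20 (16.9 with inverse-variance weights). For preschool the slope is 85/20 = 4.25, a gain of 8.5 against 10 (8.0 weighted). Sampling noise can bend the fit only the other way, so the simulated means fall further.

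**Simulated gain from 400 mg to the top dose, in points.**

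| | *T. trichiura* school-age/adult | *T. trichiura* preschool | Hookworm school-age/adult | Hookworm preschool |
|---|---|---|---|---|
| True gain | 20 | 10 | 30 | 20 |
| 3-parameter, cure-rate: mean | 14.1 | 6.9 | 30.5 | 17.8 |
| 3-parameter, logit: mean | 18.9 | 9.9 | 26.2 | 15.9 |
| Median difference, these two fits | 3.4 | 2.3 | 3.9 | 2.8 |
| These two differ by more than 10 | 19% | 5% | 6% | 2% |
| Median max-min, sigmoid fits added | 6.6 | 5.6 | 6.4 | 5.0 |
| RMSE, 3-parameter cure-rate | 8.1 | 4.2 | 6.8 | 5.5 |
| RMSE, quadratic | 10.5 | 7.3 | 8.6 | 8.1 |

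**Yardstick.** The standard error of the raw contrast is √[(p₁(1 − p₁) + p₂(1 − p₂))/38]:

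- *T. trichiura* school-age/adult: √[(0.16 + 0.24)/38] = 10.3 points
- *T. trichiura* preschool: √[(0.16 + 0.21)/38] = 9.9
- Hookworm school-age/adult: √[(0.25 + 0.16)/38] = 10.4
- Hookworm preschool: √[(0.25 + 0.21)/38] = 11.0

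The difference between the two 3-parameter fits is 2.3/9.9 = 0.23 to 3.9/10.4 = 0.38 of these. The fitted gain itself is less variable: for the hookworm logit fits its SD is 7.8 and 6.2, so there the ratio is 3.9/7.8 = 0.50 and 2.8/6.2 = 0.45. Even the biased *T. trichiura* fits have a smaller RMSE (8.1 and 4.2) than the unbiased raw contrast (10.3 and 9.9).

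**Sigmoid fits.** A sigmoid Emax has four parameters. All three *T. trichiura* cohorts and hookworm preschool have four arms, so there the sigmoid is saturated and largely follows the observed arm rates, which section 7.3 already plans to calculate.

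**ED50 limit.** The 3-parameter cure-rate fit ends on the wide limit in 68%, 75%, 14% and 42% of trials. The missing 200 mg arm is not the cause: *T. trichiura* preschool has that arm and reaches the limit most often. The cause is a near-straight planning curve. At ED50 = 16,000 mg the rise from 400 to 800 mg is 800/16,800 − 400/16,400 = 0.0232 against 0.0244 from 0 to 400 mg, which is a line in practice.

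**Fitting method.** Taken alone it moves the gain by 0.3 to 0.9 points. With 5% cure on placebo, no cures occur with probability 0.95³⁸ = 14% per cohort and 1 − 0.858⁶ = 60% in at least one of six. That troubles only methods based on arm summaries. Section 4.4 reports moderate cure on placebo in earlier work; at an assumed 15%, 0.85³⁸ = 0.2% per cohort, about 1% over six.

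**Other true curves.** If the true curve flattens earlier, the four-fit spread has a median of 1.5 (*T. trichiura* 30% at 400 mg rising to 40%), 0.4 (*T. trichiura* plateau at 30%), and 5.3 and 3.3 (hookworm school-age/adult and preschool, Emax with ED50 200 mg).

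**The case for a change.** The strongest case for a change is that the omission is plain, concerns the primary endpoint, and could be closed with a few words. The four-fit spread of 5 to 7 points reproduces in separate simulations, and it exceeds 10 points in 14–35% of trials. For *T. trichiura*, the bootstrap 95% interval for the gain from a 3-parameter cure-rate fit covers the truth in only 66–68% of trials. The lack of blinding at the site adds room for a choice made after the fact.

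The omission and the *T. trichiura* bias of that one fit stand. The rest is weaker:

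- The 5 to 7 points is a max-min over four fits, which can only grow as fits are added, and two of the four are saturated in most cohorts.
- The gain from 400 mg to the top dose is not an estimand in the plan. The plan predicts the curve, and fitted cure rates at the trial doses differ across all four fits by a median of only about 2 to 3 points, inside the 10-point target.
- Fixing the scale does not remove the cost. The cure-rate scale is low by 20 − 14.1 = 5.9 and 10 − 6.9 = 3.1 points for *T. trichiura*; the logit scale is low by 30 − 26.2 = 3.8 and 20 − 15.9 = 4.1 for hookworm.
- A quadratic check has a higher RMSE than the cure-rate Emax in every cohort type, and it falls above 400 mg in 15–45% of trials under the flatter curves. A lack-of-fit test at the 10% level flags only 13–18% of logit fits and 14–34% of cure-rate fits.

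**Conclusion.** No change follows. Section 7.3 lacks detail but states no wrong rule. For one cohort the open choice between 3-parameter fits is worth a median of about 2 to 4 points in the gain above 400 mg. It is worth about 5 to 7 points as a max-min spread if sigmoid fits are counted, and mostly less if the true curve flattens early. These amounts are small beside a raw-contrast standard error of 10 to 11 points and, for the curve itself, beside the plan's 10-point precision.

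The one reading with a material bias is the 3-parameter form on the cure-rate scale for *T. trichiura*. The arm cure rates that the plan already calls for give readers a model-free comparison, although with 38 per arm they would not prove a misfit. Choosing between scales is a fair trade-off, because each suits one parasite, and the extra curve and test would bring little.

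This rests on the planning rates in section 7.2, 38 evaluable per arm, and the assumed ED50 and Hill limits. A tighter ED50 limit on the cure-rate scale would enlarge the spread: allowing a limit of 1.5 times the top dose as well raises the medians to 7.2–10.7 points. Nothing in the documents imposes such a limit.

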4.6. Schedule of visits

	Screening					Follow up
	-28 to -1		Hours			2-3 weeks
	days	0		1-8	24	
Informed consent	Х					
Diagnosis (stool examination)	×		ent			×
Demographics	X		Randomization and treatment			
Medical history		Х	and t			
Clinical examination		Х	ation			
Biochemical parameter		Х	domiz			X
PK sampling		Х	Rand	Х	X	
Capturing AEs				X (3h)	X	x
Capturing SAE				X (3h)	X	Х

5. Selection of the trial subjects

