6.1. Adverse event definitions

The term "adverse event" could include any of the following events which develop or increase in severity during the course of the study, after administration of the study product:

- a) Any unfavourable and unintended signs, symptoms or disease temporally associated with the use of a medicinal product, whether or not considered related to the condition under study and the study product;
- b) Any abnormality detected during physical and clinical examination and whole blood analysis.

The medical conditions present at the initial trial visit that do not worsen in severity or frequency during the trial will not be defined as adverse events but be considered baseline medical conditions.

The observation time for adverse events starts when the treatment is initiated until the last follow-up examination (21 days after drug administration).

These data will be recorded on the appropriate CRF sections, regardless of whether they are thought to be associated with the study or the drug under investigation. Associated with the use of the drug means that there is a reasonable possibility that the event may have been caused by the drug (see also relatedness definitions below).

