6.2. Methods of recording and assessing adverse events

Subjects will be kept for observation for at least 3 hours following treatment for any acute adverse events. If there is any abnormal finding, the local study physician will perform a full clinical and physical examination and findings will be recorded. An emergency kit will be available on site to treat any medical conditions that warrant urgent medical intervention. Adults, school-aged children and the mother of preschool-aged children will also be interviewed 3 and 24 hours after treatment and at follow-up (2-3 weeks after treatment) about the occurrence of adverse events (see chapter 4.6).

Information on all adverse events (onset, duration, intensity, seriousness and causality) will be immediately entered in the appropriate adverse event module of the case report form (CRF) that serves as source document. For all adverse events, sufficient information will be pursued and/or obtained so as to permit i) an adequate determination of the seriousness of the event (i.e. whether the event should be classified as a serious adverse event); ii) an assessment of the casual relationship between the adverse event and the study treatments and iii) an assessment of intensity of adverse events will be judged by the study physician.

All serious adverse events or SUSARs must be reported as described in Section 6.3.

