Adverse events will be evaluated descriptively as the difference of proportion reporting adverse events before and after treatment.

If possible, a sensitivity analysis will be conducted where double infections enrolled in one trial will be included in the other trial.

8. Data management and data quality control

The investigators are responsible for an adequate data quality. Prior to the initiation of the study, a short investigators meeting will be held with the investigators and their study coordinators and a member of the Swiss TPH. This meeting will include a detailed discussion of the protocol, performance of study procedures, CRF completion, specimen collection and diagnostic methods.

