8.1. Data collection

The data produced from this research project will fall into the following categories:

- Eggs counts of hookworm, Ascaris lumbricoides and Trichuris trichiura found in participants' stool samples using the Kato-Katz technique before (baseline) and after (follow-up) treatment.
- 2. Personal information such as name, age and gender of trial participants.
- Anthropometric and clinical characteristics of the trial participants collected using the study's case report form (CRF) such as weight, height, blood pressure, temperature hemoglobin levels, any abnormal medical condition or chronic disease.
- 4. Number and type of adverse events registered in the CRF and actively probed for 3and 24,hours after treatment. The same data will be collected during the collection of the first sample at follow-up.
- 5. Pharmacokinetic parameters such as Cmax, AUC or tmax analyzed from dry blood spots or Mitra® at 0, 1, 2, 3, 4, 6, 8, 24 hours post-dosing.

Data from categories 1-4 will be paper-captured and subsequently doubled entered (data entry SOP) into ACCESS data entry masks by two independent people for quality assurance. Both databases will then be cross-checked using the Data Compare utility of Epilnfo; any discrepancies will be corrected by consulting the hard copy. Data entered into ACCESS databases will only be accessible to authorized personnel directly involved with the study by use of a password. Data in category 1 will be saved both in .mdb, .xlsx and .csv. Data in category 2, 3 and 4 will be double-entered using an Epilnfo mask and saved in .mdb, .xlsx and .csv. All categories will be merged into a single master filed saved in .xlsx and .csv. Data will then be analysed as described in section 7. PK parameters derived from analyzing microblood samples will be merged and saved as a .xlsx file. Hard copies of the data such as parasitological sheets and CRFs will remain at IHI. Digital copies along with the databases will be transferred to the Swiss TPH after a Material Transfer Agreement has been signed by both the Swiss TPH and CSRS. All data is expected to not exceed 5GB.

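### The adverse-event analysis commits to no comparison with placebo or across doses, and its pre-treatment term is inconsistently defined

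*Combined protocol and SAP*

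**What the plan says.** Section 7.3 gives one sentence on the analysis of adverse events: "Adverse events will be evaluated descriptively as the difference of proportion reporting adverse events before and after treatment". Nothing else in the document supplies a method. The same section limits the dose-response models to cure rates and egg reduction rates, section 8.1 refers all analysis to section 7, and the statistics part of the synopsis does not mention adverse events.

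The synopsis states safety of ascending doses as an objective, and section 3 lists safety and tolerability in the three age groups as a secondary objective. Section 10.6 gives each cohort a placebo arm.

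On timing, section 6.1 defines adverse events as those "which develop or increase in severity during the course of the study, after administration of the study product", and adds: "The observation time for adverse events starts when the treatment is initiated". Conditions present at the first visit that do not worsen are classed as baseline medical conditions. Section 6.2 has participants or mothers "interviewed 3 and 24 hours after treatment and at follow-up (2-3 weeks after treatment) about the occurrence of adverse events". Section 8.1 lists "Number and type of adverse events registered in the CRF and actively probed for" at 3 and 24 hours, and again at the first follow-up sample. The row "Capturing AEs" in section 4.6 marks the same three times.

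Three other places point to pre-dose information. The synopsis (Measurements & procedures) has participants "interviewed before treatment, 3 and 24 hours after treatment" and at follow-up. The introduction to section 6 includes baseline medical conditions in the safety analysis. Section 6.1.4 reports serious adverse events from consent onwards.

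**The concern.** There are two linked problems.

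First, the stated quantity is a change over time. The design offers a better comparison, because in every cohort a randomised placebo arm shows what happens without the drug over the same interval. The plan does not commit to using that arm for safety, or to showing whether events rise with dose.

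Second, one of the two proportions to be subtracted has no settled meaning. An analyst who follows section 6.1 sets it to zero. An analyst who follows the synopsis uses pre-dose symptoms. The same data then give different safety results.

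At stake is the answer to a secondary objective of a dose-ranging trial: whether higher doses are less well tolerated, and whether reported events exceed those on placebo.

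**Working it through.** **1. Arms available for a contrast.** From section 3, the *T. trichiura* cohorts have 4 + 4 + 4 = 12 arms and the hookworm cohorts 4 + 5 + 5 = 14. Section 7.2 gives 40 per arm, so 26 × 40 = 1040, which reproduces the stated total (480 + 560 in section 4.3.1). By dose: placebo 240, 200 mg 160, 400 mg 240, 600 mg 240, 800 mg 160. Every active arm has a concurrent placebo arm of 40 in its own cohort.

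**2. What the pre-treatment term can mean.**

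| Place | Implication |
|---|---|
| 6.1, definition and observation window | No adverse event can precede dosing, so the proportion is 0 |
| 6.1, baseline conditions | Unchanged prior complaints are not adverse events |
| 4.6, 6.2, 8.1 | Capture at 3 h, 24 h and follow-up only |
| Synopsis, Measurements & procedures | Interview before treatment as well |
| 6, introduction | Baseline conditions are part of the safety analysis |
| 6.1.4 | Serious events count from consent |

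The laboratory part shows the same tension. Section 6.1 includes "Any abnormality detected during physical and clinical examination and whole blood analysis", and section 4.3.1 schedules biochemistry before treatment and at 14 to 21 days. A pre-dose abnormality is therefore observable, but under the definition it is not an adverse event unless it worsens.

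**3. What the stated figure measures.** Let *b* be the pre-dose proportion (the same in both arms in expectation, by randomisation), *c* the post-dose proportion on placebo and *a* the post-dose proportion on active drug. Take the difference as after minus before.

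- Stated figure for the active arm: *a* − *b*
- Randomised risk difference: *a* − *c*
- Gap between them: (*a* − *b*) − (*a* − *c*) = *c* − *b*

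The active arm's figure, taken alone, equals the drug effect only if the placebo proportion does not change over time (*c* = *b*). The documents give no adverse-event rates, so all rates below are assumptions.

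| *b* | *c* | *a* | Stated, active | Stated, placebo | Risk difference | Gap |
|---|---|---|---|---|---|---|
| 0 (section 6.1 reading) | 5% | 5% | +5 | +5 | 0 | +5 |
| 0 | 10% | 20% | +20 | +10 | +10 | +10 |
| 0 | 20% | 30% | +30 | +20 | +10 | +20 |
| 0 | 30% | 30% | +30 | +30 | 0 | +30 |
| 10% (pre-dose symptoms) | 20% | 30% | +20 | +10 | +10 | +10 |
| 20% | 20% | 30% | +10 | 0 | +10 | 0 |
| 30% | 20% | 30% | 0 | −10 | +10 | −10 |

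With *b* = 0 the gap is the whole background rate. With pre-dose symptoms it can have either sign, or vanish.

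**4. Precision of the contrast with placebo.** The 95% half-width is 1.96 × √[(*c*(1 − *c*) + *a*(1 − *a*))/*n*]. For 10% v 20% at *n* = 40 this is 1.96 × √(0.25/40) = 15.5 points.

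| *n* per group | 5% v 10% | 10% v 20% | 20% v 30% |
|---|---|---|---|
| 40 (one cohort) | 11.5 | 15.5 | 18.9 |
| 38 (after 5% loss) | 11.8 | 15.9 | 19.3 |
| 160 (800 mg, four cohorts) | 5.7 | 7.7 | 9.4 |
| 240 (400 or 600 mg, six cohorts) | 4.7 | 6.3 | 7.7 |

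The last two rows assume one rate across cohorts. These figures describe the remedy, not the size of the defect.

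**The case against.** The strongest defence is that the sentence is silent on arms and does not exclude them. Section 7.3 describes egg counts before and after treatment by arm, and section 4.4 explains that placebo control is there to limit bias. A by-arm table is therefore a natural reading, and from such a table the randomised contrast follows under either meaning of the pre-treatment term: 30 − 20 = +10, or 0 − (−10) = +10. This stands. A reader might infer that the plan discards its placebo arms or makes the drug effect unrecoverable, and the documents do not support that. What is missing is the commitment to the comparison.

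It may also be said that the pre-treatment proportion is not really zero, because the synopsis, section 6 and section 6.1.4 all look to the time before dosing. This stands too. Zero is the consequence of section 6.1, not the only reading; the supportable claim is that the term is inconsistently defined.

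The case with 30% before dosing falling to 20% on placebo is constructed. Nothing in the documents shows that symptoms would resolve, and acute systemic illness is an exclusion. That is why a range is shown, including one row with no gap.

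Finally, the summary is only descriptive, and per-cohort intervals would be wide. Both are true, but a descriptive summary still needs a defined numerator and comparator.

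**Conclusion.** The concern holds in a limited form. The only adverse-event rule is a before/after difference that commits to no comparison with placebo or across doses, and the sections disagree on whether anything is captured before dosing. Read alone, an arm's figure differs from the randomised risk difference by *c* − *b*. Over the assumed rates this runs from −10 to +30 points, and is zero where the placebo proportion does not change.

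The conclusion about wording and definition rests on the text alone; only the sizes depend on assumed rates. It affects a secondary objective. It should be corrected before analysis, but it does not touch the sample size or the cure-rate analysis.

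**What to change.** Replace the sentence in section 7.3 with:

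> The proportion of participants with at least one treatment-emergent adverse event (new or worsened relative to baseline, section 6.1) will be summarised descriptively by arm within cohort, by severity and relatedness, with the risk difference versus the cohort's own placebo arm and 95% CI. A cohort-stratified summary by dose may be added, using only cohorts that contain that dose.

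Treat pre-dose symptoms as baseline conditions. Reconcile the synopsis (Measurements & procedures) and sections 4.6, 6 (introduction), 6.1, 6.1.4, 6.2, 7.3 and 8.1 on what is captured before treatment. The stratified summary is optional.

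The cost is a few lines of analysis text. The arms, the post-dose interviews, the intensity and causality fields and the pre/post biochemistry already exist. If the synopsis interview is kept, the visit schedule, and possibly the CRF, need a matching pre-dose symptom entry. The price in interpretation is wide per-cohort intervals, which should be reported as such.
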